Many of the women experience severe menstrual pain, yet undermanage their pain level by not taking a sufficient amount of NSAIDs. Notably, biochemical analyses demonstrate that the administration of naproxen prior to the initiation of the COX-2 cascade results in nearly complete suppression of prostaglandin synthesis; attempting to block synthesis afterwards only leads to a gradual and incomplete suppression.¹ The single, but underpowered trial, comparing menstrual pain relief between prophylactic versus response use to pain with ibuprofen did not find a difference.² It is possible that differences in prophylactic use of naproxen and ibuprofen could be due to different preferential binding to COX-1 and COX-2 receptors. Aside from this trial, clinical investigators have not sufficiently investigated prophylactic use of NSAIDs prior to the onset of menses. Although an educational trial regarding prophylaxis did demonstrate increased patient knowledge, reduction of menstrual pain was not evaluated.³ Therefore, in the present study we will establish whether prophylactic and adequate dosages of Naproxen are capable of reducing menstrual pain more than response use. Secondly, we will establish whether reduction of menstrual pain with optimized naproxen use can reduce bladder pain via cross-organ sensitization or central sensitization. We hypothesize that cross-organ sensitization (COS) is the mechanism by which dysmenorrhea may lead to some forms of chronic pelvic pain. Uterine inflammation during menstruation likely contributes to chronic pelvic pain (CPP) by triggering neurogenic inflammation in adjacent organs.⁴ This COS has been demonstrated with experimental injury and infection in animal models.^{5,6} Our prior findings discussed above^{7,8} motivate our present central hypothesis: *dysmenorrhea produces CPP via repetitive COS episodes.*

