In our ongoing study looking at the relationship between dysmenorrhea, COS and CPP (EH13-094), we planned to determine whether oral contraceptive pills (OCPs), by alleviating menstrual pain could reverse the development of COS. However, our interim analyses of participants in this study identify that many are unwilling to initiate OCPs due to the perceived side effects and fear of hormones. Other interventions to reduce the development of COS also plausibly exist, notably NSAIDs. Therefore, we propose to re-enroll many of the participants from EH13-094 who gave permission for future contact. We will utilize their baseline assessment visit data in order to establish whether naproxen can improve menstrual and bladder outcomes. After consent, prior data will be linked with the current study. We will also open this study to new participants who will be asked to perform a baseline visit (bladder test, pressure tests, EEG, questionnaires and blood draw). Participants will be invited to an open label (non-randomized) prospective trial of naproxen. After six to eight months of diary data, urine monitoring, and blood samples, a repeat visit (bladder test, pressure tests, EEG, questionnaires, and blood draw) will be conducted. The majority of the testing details below have been previously approved for the ongoing study EH13-094.

Additionally, we will investigate whether mechanisms involved in pain sensitivity predict responses to effectiveness of NSAID treatment for menstrual or bladder pain. Several studies identify that women with menstrual pain have central sensory processing abnormalities akin to what is observed in women with chronic pelvic pain states.⁹⁻¹¹ Focused investigation into gynecological risk factors for bladder pain syndrome is of particularly high value, as it more commonly affects women¹², and current treatments, such as pentosan polysulfate,¹³ amitriptyline,¹⁴ or cystoscopic hydrodistension¹⁵ are only modestly effective. The limited efficacy of these treatments reflects the multifactorial mechanisms underlying BPS, particularly in later stages, which may include cross-organ sensitization, central nervous system sensitization, mucosal inflammation, and neuropsychological factors.¹⁶ One underlying hypothesis for this finding is that repetitive episodes of

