At the screen, baseline and follow-up visit (either in person or over the web using a REDCAP, secure interface) participants will complete the following questionnaires: a) complete medical, surgical, and gynecological history, and b) a psychosocial assessment using short-form PROMIS instruments (pain behavior, pain interference, fatigue, sleep, anxiety, depression, physical function, satisfaction with participation in social roles, and 10 item global health scale).²⁰ Participants will also complete the following pain rating questionnaires (the Interstitial Cystitis Problem and Symptom Indices, the Pain Catastrophizing Scale, Revised Short-form McGill Pain Inventory⁷² and MIDAS headache questionnaire).⁶⁷ These scales have been linked to pain intensity and quality of life

in CPP sufferers, and catastrophizing (rumination, magnification, and feelings of helplessness about pain) is a well-validated intervention target for many cognitive-behavioral approaches for chronic pain.²¹⁻²⁴ Validated, CPP-specific assessment tools will be used to characterize IBS (Rome III criteria)²⁵ and bladder pain symptoms (Genitourinary Pain Index).²⁶ Subjects will also complete the Female Sexual Function Index (FSFI)⁶⁸ and Brief Symptom Inventory (BSI)- based questionnaire containing 6 somatization questions selected from the BSI-18⁶⁹ plus a vision question, and the Complex Medical Symptoms Inventory (CMSI)-General, Fibromyalgia Symptoms, Fatigue, and Vulvodynia sections.^{70,71}

Rapid Bladder Test

At the screen visit, all participants will be asked to undergo a “rapid bladder test.” Participants will be asked to rate their bladder pain on a 0-100 VAS scale when they reach “first urge.” If a participant arrives to the visit already at first urge, we will have them rate their pain and if not ≥ 10 we will wait 15 minutes past first urge and have them rate their pain again. This is because the participant may not have been focusing on the feeling of their bladder. Participants not already at first urge will be encouraged to drink water (at least 20 oz) during the screening visit until they reach first urge at which point a pain rating will be attained. After they reach first urge, they can go to the bathroom and leave their urine sample.

Pelvic Floor Exam:

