The baseline and follow-up visit includes internal vaginal pressure-pain threshold testing, which is similar in nature to the pelvic floor portion of a gynecological exam. Thus, for participants who have never had a gynecological exam, a study nurse or study doctor may complete a simple exam of the pelvic floor at the screen to promote understanding of the internal vaginal pressure-pain threshold testing that will be completed at the baseline and follow-up visit. This ensures that the integrity of our data is not biased by unfamiliar experience. Participants will be asked whether they have ever had a gynecological exam on the phone screen and a simple exam of the pelvic floor for those that say they have never had an exam will be scheduled into their screen.

Creatinine Test:

A creatinine test will be conducted to check for kidney function for all participants. This will be done via blood draw at the screen visit.

Menstrual Diaries:

All participants will be asked to complete daily diaries for a full menstrual cycle to assess their baseline scores.

[figure not shown]
Baseline Visit:

A baseline visit will be performed for all participants that have not conducted an assessment visit for EH13-094 in the last 12 months: **[Note all of these assessments are the same as the assessments approved in EH13-094]**. The baseline visit will be scheduled to occur during the luteal phase (15 to 25 days after the start of the prior menstrual cycle). Participants will be asked to confirm that menstrual pain or bleeding has not started during the baseline visit.

Food: Baseline Visits are very long so we will offer snacks to the participants (e.g., teddy grahams and fruit roll-ups).

Instrumentation: During the baseline visit, EMG and EKG electrodes, and respiratory rate monitors will be applied and information will be recorded throughout the visit. EMG leads will be placed on the lower abdomen during the bladder testing to measure muscular recruitment. The abdominal EMG leads will be moved to the knees once the bladder pain test is completed. The EKG leads and respiratory belt are placed to measure autonomic activity. The autonomic activity will be recorded to verify nociceptive experience. During each testing session, participants will also have their blood pressure and pulse taken.

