Bladder pain test: All participants will first undergo bladder pain testing described in our validation study⁷. Subjects will be provided directions for the bladder study. The bladder study involves voiding and obtaining baseline measurements of bladder volume with a 3D ultrasound abdominal transducer (GE Voluson 750, Wauwatosa, WI). After hydration with 20 oz of water, participants are instructed to report when they reach standard levels of bladder urgency: first sensation, first urge, and maximum tolerance and volumetric measurements of the bladder will be made. At each of these time points and every 15 minutes, 0-100 VAS measurements of pain and urgency are recorded. After scanning at maximum tolerance, subjects will urinate in a graded toilet hat to allow for measurement and saving a urinary specimen. Samples will be banked for analyses. If the participant gives permission in the consent form, urine samples will continue to be stored after the study is completed for possible future analyses by our lab on women's health conditions. If the participant does not give permission in the consent form for analyses beyond the current study, their sample will be destroyed upon study completion.

Pressure Pain Threshold Test: Participants will undergo body and pelvic floor pressure pain threshold testing following the same validated protocols in our published studies^{27,28} using digital external and internal vaginal pressure algometers. The body algometer (for example models see www.paintest.com) is a commonly used hand-held device in pain research that measures the

amount of pressure applied to a 1 cm² circular rubber tip. The vaginal algometer consists of 2.5 cm² circular force sensitive resistor, which fits over the pad of the examiner's index finger under an exam glove (Detailed documentation was provided in a separate earlier supplement to the IRB). Prior to evaluation, subjects will report their baseline pain on a NRS 0-10 scale and will be asked to identify any painful body sites.

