Urine: Participants will be told that urine samples will allow us to verify they are taking the study medication as directed. Participants will be asked to freeze urine collected from the evening of day 2 of their menses for each cycle. 6 storage vials will be provided. The urine samples will allow us to verify if participants are taking the provided pills.

Blood: Participants will be instructed to arrive at Evanston Hospital for a scheduled blood draw 1.5-3 hours after ingesting naproxen pills. This will allow us to verify naproxen is sufficiently absorbed to provide therapeutic effects. Only one naproxen absorption blood draw will be performed per participant. Participants will be allowed to choose the most convenient period day for testing, but cannot come on the first day.

Follow up visit:

Six to eight months later, participants will be invited to return for a follow-up visit. Participants will perform the same measurements obtained in the original baseline visit. In the event participants are unable to return for a complete baseline visit, participants will receive a prorated stipend for partial

completion of items (including questionnaires). Participants will bring in any unused study medication to this visit.

Power Analysis/Data Analysis:

The primary outcomes are menstrual pain and bladder pain. Menstrual pain will be evaluated by comparing diary data and questionnaire data from baseline to 6-8 months after treatment. We estimated the needed sample size with a power analysis. Historically, the effects of NSAIDS are known to have a large effect size ($dz > .7$). A power analysis ($\alpha=.05, 1-\beta=.80$) suggests that to detect a more moderate effect of $dz=.7$ sample size of 20 would be needed. To account for a ~20-30% drop out rate, we will recruit 30 participants.

An additional primary outcome is bladder pain as measured by the experimental bladder pain test and the GUPI questionnaire. We estimated the needed sample size with a power analysis. The effects of oral contraceptives on bladder pain had enormous effect size ($dz=2.9$). Unfortunately, too few participants were willing to take oral contraceptives. A power analysis ($\alpha=.05, 1-\beta=.80$) suggests that to detect a more moderate effect of $dz=1$ sample size of 10 would be needed. We will attempt to attain a sample size of $n=20$ to allow detection of and even lower effect size $dz=0.7$ (per the primary outcome for menstrual pain).

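### Two primary outcomes, each with two measures and each sized at the full alpha of .05, have no lead measure, testing order or success rule

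*Combined protocol and SAP*

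**What the plan says.** The Power Analysis/Data Analysis section opens: "The primary outcomes are menstrual pain and bladder pain". On the first it says: "Menstrual pain will be evaluated by comparing diary data and questionnaire data from baseline to 6-8 months after treatment". On the second: "An additional primary outcome is bladder pain as measured by the experimental bladder pain test and the GUPI questionnaire".

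Each outcome has its own sample-size calculation at alpha .05 and 80% power: 20 participants for menstrual pain at dz=.7, and 10 for bladder pain at dz=1. The plan then aims for 20 for bladder pain as well, so that dz=.7 can be detected. It recruits 30 to allow for about 20-30% dropout.

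Other sections describe how the measures are collected:
- Menstrual Diaries: "All participants will be asked to complete daily diaries for a full menstrual cycle to assess their baseline scores". During treatment, the diary is filled in on each day of bleeding or pain, and it rates bladder pain as well as menstrual pain.
- Bladder pain test: three urgency levels are marked, and "At each of these time points and every 15 minutes, 0-100 VAS measurements of pain and urgency are recorded".
- Questionnaires: a long list of instruments, none identified as the source of the menstrual-pain score.

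The available text states no statistical test, lead measure, diary or bladder-test summary, testing order, multiplicity adjustment or success rule.

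**The concern.** When two outcomes are each tested at .05 and either may carry the claim, the overall chance of a false positive exceeds .05. Here each outcome also has at least two measures, and each measure can be summarised in several ways: by day, cycle, peak or mean for the diary, and by urgency level or time point for the bladder test. As written, the primary result could be chosen after the data are seen.

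This matters even in a small study, because the plan sizes itself by formal hypothesis tests and its background section says it will establish effects on both kinds of pain. A significant result could not be read at its nominal level unless the measure and the decision rule were fixed beforehand.

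**Working it through.** **Inputs from the plan (Power Analysis/Data Analysis).** Two primary outcomes, two named measures each; alpha .05 and power .80 for each outcome; n=20 at dz=.7; n=10 at dz=1; 30 recruited; 20-30% dropout. **Assumptions.** Paired t-tests, normal changes, and correlations between measures (the plan gives none). Simulated figures use at least 200,000 trials per setting.

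**1. The plan's sample sizes.** Power comes from the noncentral t with n-1 degrees of freedom and noncentrality dz x sqrt(n), two-sided .05.
- dz=.7: n=19 gives 82.3%; n=20 (noncentrality .7 x sqrt(20) = 3.13) gives 84.4%. The stated 20 is adequate.
- dz=1: n=10 (noncentrality 3.16) gives 80.3%. The stated 10 is reproduced.
- One-sided tests would need only 15 and 8, so two-sided tests fit better. The plan does not state sidedness.
- Completers: 30 x .70 = 21 to 30 x .80 = 24.

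**2. No mean change in either outcome, either may count, n=20.**
- One test per outcome, independent: 1 - .95^2 = 9.75%. Simulated at correlations .3, .5, .7 and .9: 9.6%, 9.2%, 8.4% and 7.1%.
- Any of four measures, independent: 1 - .95^4 = 18.5%. With assumed within/between-outcome correlations of .5/.3, .7/.5 and .7/.7: 16.9%, 14.8% and 13.4%.
- Counting only false claims of benefit, one test per outcome: 4.9% at correlation 0, falling to 3.6% at .9. A single two-sided test gives 2.5%.

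**3. Menstrual pain truly changes (dz=.7), bladder pain does not, n=20.**
- One bladder test: 5%.
- Either of two bladder measures: 1 - .95^2 = 9.75% if independent, about 8.4% at correlation .7.
- Both outcomes required, either measure of each allowed: about 9.5% with independent measures, falling to about 6.4% with all correlations at .7.

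**4. Both outcomes required, one measure each, no change in either.** 0.3% to 2.9% over correlations 0 to .9. There is no inflation, but only because one measure is fixed for each outcome.

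**5. Power under a stated procedure, dz=.7, correlations 0 to .7.** Holm tests the smaller p-value at .025 and, if that succeeds, the other at .05.

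| Completers | Holm, both respond (each outcome) | Holm, only one responds | Fixed sequence, menstrual pain | Fixed sequence, bladder pain |
|---|---|---|---|---|
| 20 | 80-82% | 75% | 84% | 71-77% |
| 21 | 83-84% | 78% | 86% | 74-79% |
| 24 | 88-90% | 84% | 91% | 82-85% |

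**The case against.** The strongest reply is that the no-change scenario is unlikely. The plan expects a large NSAID effect, and in a design described as "Participants will be invited to an open label (non-randomized) prospective trial of naproxen", selection for pain of at least 5/10 and expectancy could also shift the mean. If menstrual pain changes for any reason, only the bladder null remains, and one bladder test carries 5%. This stands for the two-outcome count. It does not answer the choice between two bladder measures, which still carries more than 5%.

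A second reply is that the plan seeks reduction, so counting false worsening overstates the risk. With one test per outcome, false claims of benefit indeed stay below 5%. They are still roughly double the 2.5% of a single two-sided test at its worst.

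A third is that some ordering exists: bladder pain is called additional, and the background section says: "Secondly, we will establish whether reduction of menstrual pain with optimized naproxen use can reduce bladder pain via cross-organ sensitization or central sensitization". That orders the aims. It does not say that bladder pain is tested only if menstrual pain succeeds.

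A reader might infer that the trial's error rate is 9.75% or 18.5%. The documents do not support that. They never say that either outcome, or any measure, suffices; each figure holds under its own reading and is reached only with independent tests. Nor is 9.75% a ceiling for the plan, since it presumes one test per outcome. Conversely, one might infer that requiring both outcomes removes the problem; step 3 shows that it does not while the measures stay open.

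**Conclusion.** The point holds as a gap in the decision rule. It is not evidence that a positive result would be false. With n=20, two-sided .05 tests and no mean change in either outcome, the false-positive risk is up to 9.75% with one test per outcome (about 8.4% at correlation .7) and up to 18.5% with any of four measures (about 13-17% at correlations of .3 to .7). If menstrual pain responds, the open choice of bladder measure alone leaves roughly 6-10%, whether or not both outcomes are required. The correlations are assumptions.

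These figures describe chance findings only. Regression to the mean and expectancy in an open-label single arm are a separate limitation that alpha control does not cure. The detectable correlation of 0.38 in the same section also raises a question of sidedness, but it concerns a secondary outcome and should not be read as showing that the primary tests are one-sided. The sample sizes for the primary outcomes are adequate for the single tests they assume.

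**What to change.** Before analysis:

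1. Name one primary measure and one summary of it for each outcome, from data already collected. Examples are a diary summary of menstrual pain (baseline cycle against follow-up) and a bladder-test VAS summary (baseline visit against follow-up visit). The choice is the investigators'. Make the remaining menstrual and bladder measures secondary.
2. State that tests are two-sided, with familywise alpha .05 across the two outcomes by Holm. A fixed sequence with menstrual pain first is an acceptable alternative and matches the order of the aims.
3. Restate power under the chosen procedure, using the number of completers expected for the chosen measure. The Follow up visit section allows partial completion that includes questionnaires, so the bladder test may have fewer completers than the GUPI.

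Holm is the better default because, at 20 completers, it keeps both outcomes at about the plan's 80% if both respond, whereas the fixed sequence leaves bladder pain below it. Its cost is some power per outcome: from 84% to 80-82% at 20 completers if both respond, and below 80% at 20-21 completers if only one does. Under the fixed sequence, menstrual pain keeps its full power, but bladder pain cannot be claimed if menstrual pain fails. Either way the change is to analysis wording only, with no new data and no change to the 30 recruited.

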Secondary outcomes include predicting NSAID effectiveness via the investigated mechanisms. We predict impaired conditioned pain modulation and reduced pain pressure thresholds will predict NSAID effectiveness for dysmenorrhea. With $n=20$, we can detect relationships between treatment response and conditioned pain modulation or pain pressure threshold testing with a correlation coefficient (Pearson's r) exceeding 0.38.

Bibliography

3. Chiou M-H, Wang H-H, Yang Y-H. Effect of systematic menstrual health education on dysmenorrheic female adolescents' knowledge, attitudes, and self-care behavior. *Kaohsiung J Med Sci.* 2007;23(4):183-190. doi:10.1016/S1607-551X(09)70395-X
4. Wesselmann U. Neurogenic inflammation and chronic pelvic pain. *World J Urol.* 2001;19(3):180-185.

7. Tu F, Epstein A, Pozolo K, Sexton D, Melnyk A, Hellman K. A Non-Invasive Bladder Sensory Test Supports a Role for Dysmenorrhea Increasing Bladder Noxious Mechanosensitivity. *Clin J Pain.* in press.

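### The correlation of 0.38 said to be detectable with 20 women is not an 80%-power figure; at two-sided 5% and 80% power the detectable correlation is about 0.58

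*Combined protocol and SAP*

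**What the plan says.** The combined protocol and SAP deals with sample size under Power Analysis/Data Analysis. For menstrual pain it states: "A power analysis ($\alpha=.05, 1-\beta=.80$) suggests that to detect a more moderate effect of $dz=.7$ sample size of 20 would be needed". For bladder pain, a calculation with the same alpha and power "suggests that to detect a more moderate effect of $dz=1$ sample size of 10 would be needed". Recruitment is then inflated for attrition: "To account for a ~20-30% drop out rate, we will recruit 30 participants".

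The same section goes on to the secondary outcomes. It makes a directional prediction, "We predict impaired conditioned pain modulation and reduced pain pressure thresholds will predict NSAID effectiveness for dysmenorrhea". For a sample of 20 it supports this with one quantitative statement: "we can detect relationships between treatment response and conditioned pain modulation or pain pressure threshold testing with a correlation coefficient (Pearson's r) exceeding 0.38". For that statement it gives no alpha, power, sidedness or formula.

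**The concern.** The two preceding calculations in the section use the word detect in its usual sense, an effect that the study has 80% power to find. A reader will give the correlation statement the same meaning. A detectable correlation of 0.38 from 20 observations is too small for that: it is about where an observed correlation becomes significant one-sided, which corresponds to a power of roughly one half.

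The predictor analysis is a declared aim of the study, and this sentence is its only quantitative support. If the figure is taken at face value, a non-significant correlation could be read as evidence that conditioned pain modulation and pressure pain thresholds do not predict naproxen response. With 20 women the data could not support that conclusion for a correlation of moderate size.

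**Working it through.** **Inputs.** From Power Analysis/Data Analysis: n = 20; stated detectable r = 0.38; alpha = .05 and power = .80, given for the primary outcomes and carried over here as an assumption. Sidedness is not stated and has to be inferred.

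**Sidedness of the primary calculations.** Smallest n for 80% power in a paired t-test (noncentral t, alpha .05):

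| dz | n in the plan | two-sided | one-sided |
|---|---|---|---|
| 1.0 | 10 | 10 (power 0.803) | 8 (power 0.815) |
| 0.7 | 20 | 19 (power 0.823; 0.844 at n = 20) | 15 (power 0.824) |

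The dz = 1 result matches a two-sided test exactly, and the dz = 0.7 result is within one participant of it. Neither matches a one-sided test. Two-sided is therefore the likely convention of the section.

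**Where 0.38 comes from numerically.** The critical value of r is t / sqrt(t² + n − 2), with 18 degrees of freedom:

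- one-sided 5%: t = 1.734, so r = 1.734 / sqrt(3.007 + 18) = 0.378
- two-sided 5%: t = 2.101, so r = 2.101 / sqrt(4.414 + 18) = 0.444

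The first rounds to the plan's figure. Other combinations were tried: one- and two-sided, alpha .05 and .10, power .50, .80 and .90, and n = 30 at 80% power. None gives 0.38 at 80% power. The only matches are the one-sided 5% threshold and its equivalent, two-sided alpha .10 with 50% power (Fisher z: 0.379).

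**Power if the true r is 0.38, n = 20.** By Fisher z, atanh(0.38) × sqrt(17) = 0.400 × 4.123 = 1.650.

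- two-sided: Φ(1.650 − 1.960) = 0.378
- one-sided: Φ(1.650 − 1.645) = 0.502

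The exact bivariate-normal calculation gives 0.391 and 0.521, and a simulation of 200,000 samples gives 0.390 and 0.522. A true correlation of 0.38 would thus be missed about 61% of the time two-sided and 48% one-sided.

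**Correlation detectable with 80% power, n = 20.** By Fisher z, r = tanh((z_alpha + z_power) / sqrt(n − 3)):

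- two-sided: tanh((1.960 + 0.842) / 4.123) = tanh(0.680) = 0.591; exact 0.579
- one-sided: tanh((1.645 + 0.842) / 4.123) = tanh(0.603) = 0.539; exact 0.526

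A fixed-predictor model is slightly more favourable (0.552 and 0.501) but still far from 0.38.

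**n needed for r = 0.38 at 80% power.** By Fisher z, n = ((z_alpha + z_power) / 0.400)² + 3, which gives 52.04, so 53, two-sided, and 41.6, so 42, one-sided. The exact figures are 52 and 41.

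**If more than 20 women complete.** Thirty recruits with 20–30% dropout leave 21 to 24. At n = 24, Fisher z gives tanh(2.802 / sqrt(21)) = 0.545 two-sided. With all 30 the exact figures are 0.49 two-sided and 0.44 one-sided.

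**What an observed r of 0.38 would show at n = 20.** t = 0.38 × sqrt(18) / sqrt(1 − 0.144) = 1.74, two-sided p = 0.098. The 95% interval is tanh(0.400 ± 1.960 / 4.123), or −0.08 to 0.70.

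**The case against.** The arithmetic is hard to dispute; the objections concern interpretation and weight.

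- **The basis of 0.38 is not stated.** That it was taken from a critical value is an inference from the numerical match. Read literally, the sentence could describe the threshold for an observed correlation, and on a one-sided 5% test that would be correct. This stands as a caution about origin. It does not rescue the sentence as a power statement: it sits under a power heading, follows two 80%-power uses of the same verb, and does not signal a change of meaning.
- **The prediction is directional, so a one-sided test may have been meant.** No one-sided test is specified, and the primary calculations fit two-sided tests, although those are tests of a different kind. If one-sided testing is granted, the detectable correlation is about 0.53 rather than 0.58, and power at 0.38 is about one half. The stated figure is still wrong.
- **It is a secondary outcome.** This is true. The sentence did not set the sample size and changes no procedure or primary analysis. The plan also nowhere says that a null result means no prediction, so the misreading is a risk and not something the plan commits to.
- **Calling the analyses exploratory is a matter of preference.** This is fair. The essential correction is numerical.

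**Conclusion.** The figure is wrong as a detectable effect. With 20 women, 0.38 has about 39% power two-sided and 52% one-sided, against the 80% that the section implies. The correlation detectable with 80% power is about 0.58 two-sided (0.59 by Fisher z) or 0.53–0.54 one-sided.

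This rests on three assumptions: that alpha .05 and 80% power carry over from the primary calculations; that the two-sided convention inferred from them applies; and that the two variables are roughly bivariate normal. Dropping the two-sided assumption changes the size of the discrepancy but not the conclusion. None of the figures allows for testing more than one predictor, and any adjustment for that would raise the detectable correlation further. The primary sample size is not affected.

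**What to change.** Replace the correlation sentence with one that states its basis, for example:

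> With n = 20, two-sided alpha .05 and 80% power, the smallest detectable correlation is about 0.58; power for a true correlation of 0.38 is about 39%.

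If one-sided testing is intended, prespecify it and give about 0.53 and 52% instead. If 0.38 is kept, describe it as the one-sided 5% significance threshold for an observed correlation and give the power figure beside it.

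It would also help to report each correlation with its 95% confidence interval, to state that a non-significant result does not rule out a moderate correlation, and to label the predictor analyses exploratory.

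The cost is one restated sentence, a short note on interpretation and a less favourable figure. No extra participants or procedures are needed.
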